4.2.1.2. Statistical Method

With a re-randomization at the end of Year 1, the initial stratification factors from the randomization are no longer applicable in the analysis of Year 2. Therefore, the stratifications factors will be removed from the MMRM model as in the primary analysis.

The revised model is described below.

A mixed model for repeated measures (MMRM) will be applied to all available data, using response variable of the GA growth area over time up to Month 24 in 5 time points: Baseline, Month 6, Month 12, Month 18, and Month 24. The MMRM will be used to assess the difference between the treatment groups in terms of the rate of growth (slope) of the GA over time of 24 months. Time is defined as a continuous variable in number of study days since the baseline assessment. Treatment groups include ACP EM, ACP EOM, and Sham. A model will be fitted

by using restricted maximum likelihood (REML) and include time, treatment, and treatment by time interaction as fixed effects, subject as random effect.

Notice that in the primary analysis at Year 1 (Month 12), the square root transformation of GA growth area was used. However, the mean GA growth (slope) has shown similar results with or without square root transformation. In addition, it is difficult to interpret the transformed data in context. Therefore, in the Year 2 analysis, the untransformed GA growth using observed GA area of measurement will be used as the primary endpoint.

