11.3 Determination of Sample Size and Statistical Rationale

The sample size for this study is based on recently obtained 12-month results of the OPH2003 pivotal international, multicenter, randomized, double masked, sham-controlled clinical trial that was performed to evaluate the safety and efficacy of Zimura in patients with geographic atrophy secondary to AMD. The prespecified primary endpoint, mean change in GA growth over 12 months, equivalent to the mean rate of GA growth used in this study, was measured by fundus autofluorescence (FAF) based on readings at three time points (Baseline, Month 6, and Month 12) and was calculated using the square root transformation of the GA area. The FAF images were assessed by an independent masked reading center. The reduction in the mean rate of GA growth over 12 months was 0.11 mm ($p = 0.0072$) for the Zimura 2 mg group compared to the Sham control group.

In this Phase 3 trial, the primary analyses will be based on the comparison of the estimated reduction in the mean rate of GA growth over 12 months for Zimura 2 mg group versus the Sham control group. By pre-specification, this study will obtain evidence regarding the effect of Zimura on the mean rate of growth (slope) estimated based on GA area measured by fundus autofluorescence (FAF) in at least 3 time points over 12 months, when compared with Sham (square root transformation). The FAF images will be assessed by an independent masked reading center. The effect of treatment on the square root transformation of the GA area will be assessed using a mixed model for repeated measures model (MMRM) including stratification factors.

A total of approximately 400 patients will be randomized. If the 2 mg dose of Zimura truly provides a 0.11 mm reduction in the mean rate of GA growth over 12 months, then the trial will have 97% power to detect that effect at the two-sided significance level of 0.05. **Statistical**

significance at the two-sided significance level of 0.05 will be achieved for an estimated 0.057 mm reduction in the mean rate of GA growth over 12 months.

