11.5 Randomization Procedure

Patients will be centrally allocated to one of the two treatment groups by a dynamic minimization procedure using clinical site in a 1:1 ratio stratified by factors known to be of prognostic importance in AMD:

- Baseline visual acuity < 50 ETDRS letters (20/100 Snellen equivalent) vs \geq 50 ETDRS letters
- Size of Baseline geographic atrophy (< 4 disc areas vs \geq 4 disc areas)
- Pattern of Fundus Auto Fluorescence (FAF) at the junctional zone of GA (None/focal vs banded/diffuse)

Patients initially randomized to Zimura 2 mg at Day 1 will be re-randomized at Month 12 in 1:1 ratio to Zimura 2 mg monthly vs every other month (please see 11.1 Study Design) using the same minimization procedure as for the initial randomization (i.e. using the same factors at Baseline).

Randomization will be performed using an IRT system based on the stratification information above to randomize each subject and assign a treatment arm.

The IRT system will be used to assign masked study kits to patients throughout the duration of the trial. All study medication must be dispensed using the IRT system. At each dispensing visit the IRT system will allocate each study drug kit(s) using the kit number on the label of the study medication kit.

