The sample size for this study is based on the 12-month results of the OPH2003 (GATHER1) pivotal international, multicenter, randomized, double masked, sham-controlled clinical trial that was performed to evaluate the safety and efficacy of Zimura in patients with geographic atrophy secondary to AMD. The prespecified primary endpoint, mean change in GA growth over 12 months, equivalent to the mean rate of GA growth used in this study, was measured by fundus autofluorescence (FAF) based on readings at three time points (Baseline, Month 6, and Month 12) and was calculated using the square root transformation of the GA area. The FAF images were assessed by an independent masked reading center. The reduction in the mean rate of GA growth over 12 months was 0.11 mm ($p = 0.0072$) for the Zimura 2 mg group compared to the Sham control group.

A total of approximately 400 patients will be randomized in the GATHER2 trial. The effect of treatment will be assessed on the square root transformation of the mean rate of GA growth (slope) estimated based on GA area measured in at least 3 time points over 12 months, where the analysis of variance will include the stratification factors. Suppose the standard deviation for the primary endpoint in GATHER2 is as assumed in the design of the GATHER1 trial, (which is 7% higher than was actually observed in that trial.) If the 2 mg dose of Zimura truly provides a 0.11 mm reduction in the mean rate of GA growth over 12 months, then the trial will have 97% power to detect that effect when using a test statistic having (one-sided) 2.5% false positive error rate. Furthermore, the trial will have nearly 90% power to achieving an even more robust significance level at two-sided $p < 0.01$. Statistical significance at the traditional level of two-sided $p = 0.05$ would be achieved with an estimated 0.057 reduction in the mean rate of GA growth over 12 months. Note that the power of the trial will be slightly lower when using an alpha-level that would be adjusted by (two-sided) 0.001 for each DSMB meeting at which any data are reviewed.

RANDOMIZATION

Patients will be centrally allocated to one of the two treatment groups by a dynamic minimization procedure using clinical site in a 1:1 ratio stratified by factors known to be of prognostic importance in AMD:

[figure not shown]

CONFIDENTIAL

- Baseline visual acuity < 50 ETDRS letters (20/100 Snellen equivalent) vs. \geq 50 ETDRS letters

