- Size of Baseline GA (< 4 disc areas vs. \geq 4 disc areas)
- Pattern of FAF at the junctional zone of GA (none/focal vs. banded/diffuse)

Patients initially randomized to Zimura 2 mg at Day 1 will be re-randomized at Month 12 in 1:1 ratio to Zimura 2 mg monthly vs every other month using the same minimization procedure as for the initial randomization (i.e., using the same factors at Baseline).

Randomization will be performed using an IRT system based on the stratification information above to randomize each subject and assign a treatment arm.

CONFIDENTIAL

CONFIDENTIAL

DEFINITION OF POPULATIONS

The analysis and reporting of the data from this study will be performed using the following analysis populations:

Intention-To-Treat (ITT) Population

The intention-to-treat population (ITT) will consist of all randomized subjects who received at least one dose of study drug. Subjects will be analyzed in the treatment group assigned at randomization.

Per-protocol (PP) Population

The per-protocol population (PP) will consist of all ITT subjects without any significant violation of the protocol. The significant and major protocol violations will be defined prior to database lock in a masked fashion.

Safety Population

The safety population will include all subjects who received at least one dose of study drug. Subjects who have ever received an injection of Zimura during this trial will be analyzed in the Zimura group.

DEFINITION OF SUBGROUPS

The mean rate of growth (slope) estimated based on GA area measured by FAF in at least 3 time points: Baseline, Month 6, and Month 12 (square root transformation) will be displayed within the following subgroups:

- Size of Baseline geographic atrophy (< 4 disc area vs. \geq 4 disc area)
- Baseline visual acuity < 50 ETDRS letters (20/100 Snellen equivalent) vs. \geq 50 ETDRS letters
- Pattern of Fundus Auto Fluorescence (FAF) at the junctional zone of GA (None/focal vs. banded/diffuse)
- Age (<65 vs. 65 ~ 74 vs. 75 ~ 84 vs. \geq 85)
- Gender (Male vs. Female)
- Race (American Indian/Alaska Native vs. Black or African American vs. Asian vs. Native Hawaiian/Pacific Islander vs. White vs. Other)
- Ethnicity (Hispanic or Latino vs. Not Hispanic or Latino)

DATA HANDLING CONVENTIONS

General Conventions

Data will be analyzed using SAS Studio (version 3.6) or R. Descriptive analyses will be performed on Baseline, safety and efficacy data. All tables will be created by treatment arm (Zimura and Sham) and overall.

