A mixed model for repeated measures (MMRM) will be applied to all available data, using as response variable the square root of GA area measured by FAF in at least 3 time points: Baseline, Month 6, and Month 12. The MMRM will be used to assess the difference between the treatment groups in terms of the rate of growth of the square root of GA area (slope) over 12 months. Previous trial OPH2003 (GATHER1) showed the change in the square root of geographic atrophy to be remarkably linear over time. As a result, a linear model is not only convenient and easily interpretable, but it is also appropriate given the natural history of the disease. A model will be fitted by using restricted maximum likelihood (REML) and include Baseline VA (< 50 letters vs. ≥ 50 letters), and pattern of FAF at the junctional zone of GA (none/focal vs. banded/diffuse) as used in the randomization as covariates. For the model, fixed effects will include time, treatment, Baseline VA (< 50 letters vs. ≥ 50 letters), pattern of FAF at the junctional zone of GA (none/focal vs. banded/diffuse), treatment by time interaction, Baseline VA (< 50 letters vs. ≥ 50 letters) by time interaction, and pattern of FAF at the junctional zone of GA (none/focal vs. banded/diffuse) by time interaction. The model will include an unstructured modelling of within-subject correlations. If this analysis fails to converge, alternative structures (e.g., heterogeneous autoregressive, heterogeneous compound symmetry, autoregressive, or compound symmetry, in this order) will be considered. The Kenward-Roger approximation will be used to estimate denominator degrees of freedom. The test of difference between the two arms in the mean rate of growth

CONFIDENTIAL

(slope) of the square root of GA area over 12 months will be assessed by testing the appropriate contrast of the model parameter estimates.

[Redacted content]

CONFIDENTIAL

[Redacted text block]

[Redacted text line]

[Redacted text line]

[Redacted text line]

[Redacted text line]

[Redacted text line]

[Redacted text line]

[Redacted text line]

[Redacted text line]

[Redacted text line]

[Redacted text line]

[Redacted text line]

[Redacted text line]

[Redacted text line]

[Redacted text line]

[Redacted text line]

[Redacted text line]

[Redacted text line]

[Redacted text line]

[Redacted text line]

[Redacted text line]

CONFIDENTIAL

- █ [REDACTED]
- █ [REDACTED]
- █ [REDACTED]
- █ [REDACTED]
- █ [REDACTED]
- █ [REDACTED]
- █ [REDACTED]

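### Year 2 drops baseline VA group and FAF pattern from the GA slope model for a reason the randomization procedure contradicts, probably at a modest cost in precision; separately, one Year 1 stratification-error check uses a 4 mm² cut where 10 mm² was applied

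*SAP*

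**What the plan says.** **Year 2 model.** Year 2 SAP section 4.2.1.2 gives as its reason that "the initial stratification factors from the randomization are no longer applicable in the analysis of Year 2", and the Version History repeats it. The revised model has time, treatment and "treatment by time interaction as fixed effects, subject as random effect". Its response is untransformed GA area at five time points.

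**Randomization.** Protocol section 11.5 says the Month 12 re-randomization was done "using the same minimization procedure as for the initial randomization (i.e. using the same factors at Baseline"). The Randomization section of the Year 1 SAP agrees: "using the same minimization procedure as for the initial randomization (i.e., using the same factors at Baseline"). Year 2 SAP section 1.2 keeps patients first assigned to Sham on Sham, without re-randomization.

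**Year 1 model.** Protocol section 11.3 says the square-root GA area "will be assessed using a mixed model for repeated measures model (MMRM) including stratification factors". The Year 1 primary model carried baseline VA group and "pattern of FAF at the junctional zone of GA (none/focal vs. banded/diffuse) as used in the randomization as covariates", each with its time interaction. Baseline GA size, the third factor, was not in that model, so Year 2 removes two terms and their interactions, not three.

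**Timing and disclosure.** The addendum in Year 2 SAP section 5.2 already leaves the factors out. Section 1 dates its approval to 3 August 2022, before Year 1 unmasking. Section 4.5, which lists changes from the protocol-planned analyses, does not mention the removal.

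**Stratification-error check.** The Year 1 SAP section on this error plans two analyses. The first groups baseline GA size with cuts at 4 and 10 mm². The second makes one group of the patients randomized before 16 November 2020 and splits the rest at 4 mm². The same section says patients since that date were stratified at 4 disc areas, equated to 10 mm².

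**The concern.** Factors that drove the allocation normally belong in the analysis. Here they governed both steps behind EM versus Sham: the Day 1 allocation and the Month 12 split of the active arm. Protocol section 11.5 calls them prognostic, and Year 2 SAP section 4.4.1 still uses them as subgroups.

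Omitting balanced prognostic factors leaves their variance in the residual, so the reported standard error exceeds the true sampling error. EM versus Sham is the first Year 2 hypothesis, and under section 2 each later test runs only if all earlier ones are significant. Power lost there carries down the whole list.

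The 4 mm² cut is a different and smaller matter. It puts later patients with lesions of 4 to 10 mm² together with those of 10 mm² or more, which is the misplacement the check was meant to examine.

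**Working it through.** **1. Reproduce the design figure.** Protocol section 11.3 and the Year 1 sample-size section give 0.057 mm as the smallest significant difference, 0.11 mm as the design effect and about 400 patients, 1:1. No SD is printed.
- SE = 0.057/1.96 = 0.0291, so SD = 0.0291/√(2/200) = 0.291.
- Power = Φ(0.11/0.0291 − 1.96) = 96.6%, against the stated 97%. At two-sided 0.01 it is 88.6%, against the stated figure of nearly 90%.

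**2. Scale to EM versus Sham.** Splitting the active arm gives about 100 EM against 200 Sham, with no dropout assumed.
- SE = 0.0291 × √[(1/100 + 1/200)/(2/200)] = 0.0356.
- d = 0.11/0.0356 = 3.09; power = Φ(3.09 − 1.96) = 87.0%.

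**3. Remove the factors.** Let R² be the assumed share of the variance of the estimated slopes that the two factors explain, q = √(1 − R²) and k = 1/q. With balanced factors the estimate's true sampling error is unchanged, but the reported SE is k times too large. The Year 1 SAP says of the planned analysis "where the analysis of variance will include the stratification factors", but not whether its SD is net of them, so both cases are shown.
- Case A, SD already net of the factors: power is Φ(d − 1.96) with them and Φ(d − 1.96k) without.
- Case B, SD not net of them: power is Φ(d/q − 1.96) with them and Φ((d − 1.96)/q) without.

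| Assumed R² | k | A: with → without (loss) | B: with → without (loss) | Size of unadjusted test, 2Φ(−1.96k) |
|---|---|---|---|---|
| 2% | 1.010 | 87.0 → 86.6 (0.4) | 87.7 → 87.3 (0.4) | 4.8% |
| 5% | 1.026 | 87.0 → 85.9 (1.1) | 88.7 → 87.6 (1.0) | 4.4% |
| 10% | 1.054 | 87.0 → 84.7 (2.4) | 90.2 → 88.3 (2.0) | 3.9% |
| 20% | 1.118 | 87.0 → 81.5 (5.5) | 93.2 → 89.6 (3.6) | 2.8% |
| 30% | 1.195 | 87.0 → 77.2 (9.8) | 95.8 → 91.1 (4.7) | 1.9% |

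Losses are taken before rounding. The last column assumes that slope variation between patients is modelled; the omission then makes the test conservative. If the factors were not balanced between the groups, case A without them would be Φ(dq − 1.96): 86.4, 85.3, 83.4 and 78.9% at R² of 2, 5, 10 and 20%.

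**4. Stratification-error check.** No arithmetic is needed: the applied cut was 10 mm², and the second analysis uses 4 mm². The first analysis contains the 10 mm² boundary. The 38 misplaced patients (38/400 = 9.5%) were randomized before the correction. The number randomized later, whom this cut affects, is not given.

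**The case against.** **Prespecified and disclosed.** The unadjusted model was fixed before Year 1 unmasking and appears in the addendum, the Version History and section 4.2.1.2. This stands. A reader might infer that the factors were dropped after Year 1 results were seen; the dates rule that out. What remains is an unsupported reason and an omission from section 4.5.

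**Forgone power, not validity.** This largely stands. A reader might infer a raised false-positive rate, but where slope variation is modelled the omission lowers it. Year 2 names only a subject random effect, whereas for Year 1 "The model will include an unstructured modelling of within-subject correlations". The addendum refers to a similar MMRM. Whether the covariance structure changed is a separate question that arises with or without the factors, and nothing here depends on it.

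**Proxy scale.** The power figures come from 12-month square-root data, while Year 2 analyses untransformed area over 24 months. The Year 1 SAP justifies the square root as removing the dependence of growth on baseline lesion size. On the raw scale that dependence can return, so copying the two Year 1 terms alone may miss the strongest covariate. This stands, and the fix includes GA size.

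**Replacing the primary model now.** Year 1 results are known, and three of the five time points in the Year 2 slope fall in Year 1. Substituting a new primary model is therefore debatable; adding a sensitivity analysis is not.

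**BCVA.** The BCVA and LL BCVA models in section 4.2.3 also omit the factors and the baseline value. A reader might infer a breach of Protocol section 11.7.4, but that is a generic rule for efficacy endpoints, and the protocol lists both measures as safety endpoints. No specific plan is contradicted.

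**The 4 mm² cut may be a unit slip for 4 disc areas.** That is plausible, and the correction is the same.

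**Conclusion.** The point holds as a wrong rationale with a probable, mostly modest cost, and a revision is worth making. The documents themselves establish that the stated premise is contradicted, that the removal is missing from section 4.5, and that the second Year 1 check does not match the strata used.

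The size of the precision loss is not established. It rests on an assumed R², balanced factors, no dropout, slope variation being modelled, and the 12-month square-root scale standing in for 24-month untransformed area. On those terms the loss at EM versus Sham is about 0.4 to 2.4 power points for R² of 2-10%, and 4 to 10 points only at 20-30%.

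The 4 mm² mismatch affects one of two sensitivity analyses. A reader might infer that the Year 1 handling of the stratification error fails as a whole; it does not, because the first analysis is sound.

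**What to change.** 1. Before Year 2 unmasking, correct the rationale in section 4.2.1.2 and keep the prespecified unadjusted model. Add, as a named sensitivity analysis, the same model with baseline VA group, FAF pattern and baseline GA size group, each with its time interaction. List the removal in section 4.5. The sponsor could make the adjusted model primary only before Year 2 unmasking, with the unadjusted result reported beside it; after unmasking, only the sensitivity analysis remains open.
2. In the second Year 1 stratification-error analysis, split patients randomized after 16 November 2020 at 10 mm² instead of 4 mm². Year 2 SAP section 1 says the Year 1 analysis has been conducted, so this probably means rerunning one sensitivity analysis.
3. As an inexpensive supportive addition, also report the BCVA and LL BCVA models adjusted for the baseline value and the stratification factors.

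The cost is a little extra analysis and a few degrees of freedom. The variables are already collected.

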4.2.1.3. Sensitivity or Supportive Analyses

The following sensitivity or supportive analyses will be performed.

4.2.1.3.1. Miller imputation of missing data

For the analyses of the endpoint, the Mixed-Effects Repeated Measures (MMRM) analysis does not require data imputation and uses only the observed data.

Four analyses described by Miller et al. (2001) will be performed for further insight into the potential impact of missing data on the results:

1. the observed means from the active arm and the sham arm will be imputed to patients with missing data in the arm they were allocated to;
2. the average of observed means from the active arm and the sham arm will be imputed to all patients with missing data;
3. the observed mean from the sham arm will be imputed to all patients with missing data.
4. the observed means from the active arm and the sham arm will be imputed to patients with missing data in the opposite arm they were allocated to (a “cross-over” scheme);

These four sensitivity analyses make different assumptions about missing data and are likely to be increasingly biased against a true treatment effect. Therefore, they will be used only for sensitivity purposes.

4.2.1.3.2. Multiple imputation with tipping point analysis

In addition to filling a single value for the missing value at a visit as described in Miller method, multiple imputation with tipping point analysis will be conducted. Please refer to primary analysis CSR Appendix for technical details.

4.2.1.3.3. Time (visit) as a categorical variable in the MMRM model

Time will be replaced as a categorical variable in the MMRM model above with the visits (Baseline, Month 6, Month 12, Month 18, and Month 24) to assess the change from baseline over time.

4.2.1.3.4. Piece-wise analysis by every 6-month interval

The MMRM model assumes a linear growth rate of GA over time. A linear spline approximation by every 6-month interval is to provide more detail on the GA growth curve by time interval over 2 years. The MMRM model in Section 4.2.1.2 will be used to fit every 6-month interval data.

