4.1.2. Handling Missing Data in Efficacy Analyses

Methods that take into account the presence of missing data and that yield valid estimates under the assumption of data missing at random (MAR) will be used. The Mixed Model on Repeated Measures fitted by Restricted Maximum Likelihood method will be used in the mean growth GA analysis, where the observed data will be used with no imputation. Several imputation methods will be used in sensitivity analyses, whenever necessary, to impute the missing data, as described in Section 4.2.4 sensitivity analyses.

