4.2. Efficacy Analysis

4.2.1. Mean GA growth (slope): EM, EOM vs. Sham

4.2.1.1. Definition of Estimand

The objective is to demonstrate efficacy of ACP EM or EOM versus Sham in mean GA growth rate (slope) after re-randomization regardless of any non-adherence to or interruption of study treatment, and regardless of initiation of alternative treatment.

The following 5 attributes define the Estimand for the objective evaluation:

A. Population: re-randomized population

B. Interventions:

ACP EM or EOM versus Sham.

C. Endpoint:

GA area over 24 months from Baseline, Month 6, Month 12, Month 18, and Month 24.

D. Intercurrent events (ICE's) and strategies:

1. Treatment changes (i.e., interruptions, non-adherence, dose changes, discontinuation): “treatment policy” – i.e., treatment changes will be ignored, and all data collected will contribute to the analysis regardless of whether these follow such ICE's.
2. COVID-19: “treatment policy” – i.e., impact of COVID-19 pandemic will be ignored, and all data collected will contribute to the analysis regardless of whether these follow such ICE's.

E. Population-level summary:

Difference between groups (EM vs. Sham, EOM vs. Sham) in mean growth rate (slope) of the GA area over 24 months.

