4.5. Changes to Protocol-planned Analyses

The following changes are made from protocol planned analyses:

- Time to vision loss analysis based on BCVA was added after primary analysis on Year 1
- GA growth rate without square root transformation
- Piece-wise analysis by every 6-month interval on GA growth rate

5. Supporting Documentation

5.1. [Redacted] *CCI* [Redacted]

[Redacted]

[Redacted]	[Redacted]	[Redacted]
[Redacted]	[Redacted]	[Redacted]
[Redacted]	[Redacted]	[Redacted]
[Redacted]	[Redacted]	[Redacted]
[Redacted]	[Redacted]	[Redacted]
[Redacted]	[Redacted]	[Redacted]
[Redacted]	[Redacted]	[Redacted]
[Redacted]	[Redacted]	[Redacted]
[Redacted]	[Redacted]	[Redacted]
[Redacted]	[Redacted]	[Redacted]
[Redacted]	[Redacted]	[Redacted]
[Redacted]	[Redacted]	[Redacted]
[Redacted]	[Redacted]	[Redacted]
[Redacted]	[Redacted]	[Redacted]
[Redacted]	[Redacted]	[Redacted]

CCI

[REDACTED]	[REDACTED]	[REDACTED]
[REDACTED]	[REDACTED]	[REDACTED]
[REDACTED]	[REDACTED]	[REDACTED]
[REDACTED]	[REDACTED]	[REDACTED]
[REDACTED]	[REDACTED]	[REDACTED]
[REDACTED]	[REDACTED]	[REDACTED]
[REDACTED]	[REDACTED]	[REDACTED]
[REDACTED]	[REDACTED]	[REDACTED]
[REDACTED]	[REDACTED]	[REDACTED]
[REDACTED]	[REDACTED]	[REDACTED]

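### Year 2 SAP 4.2.1.3.4 calls the piece-wise analysis a linear spline but words it as separate two-visit fits, which ignore earlier growth and so bias late slopes if dropout depends on that growth

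*SAP*

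**What the plan says.** Year 2 SAP 4.2.1.3.4 describes the piece-wise analysis in two steps. The aim is "A linear spline approximation by every 6-month interval is to provide more detail on the GA growth curve by time interval over 2 years". The method is "The MMRM model in Section 4.2.1.2 will be used to fit every 6-month interval data". Section 4.5 lists it among the changes from the protocol as "Piece-wise analysis by every 6-month interval on GA growth rate".

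The model referred to, in 4.2.1.2, treats time linearly: "Time is defined as a continuous variable in number of study days since the baseline assessment". Its terms "include time, treatment, and treatment by time interaction as fixed effects, subject as random effect". It names no knots, spline basis, random slope or covariance structure.

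Three neighbouring passages matter:

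- Section 4.2.1.3.3 plans a companion model on all five visits: "Time will be replaced as a categorical variable in the MMRM model above with the visits".
- Section 4.2.1.1 sets the population: "A. Population: re-randomized population". Section 3 excludes from that set patients who left in Year 1.
- Section 4.1.2 says that efficacy methods that "yield valid estimates under the assumption of data missing at random (MAR) will be used".

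Section 4.2.1.3 places the piece-wise analysis among sensitivity or supportive analyses. It is not among the ranked hypotheses visible in Section 2.

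**The concern.** A linear spline is normally one model on all visits, with pieces that join at the knots. The 4.2.1.2 model fitted to one interval's data is a straight line through two visits, and four such fits need not join. A patient last seen at Month 12 adds nothing to the Month 18-24 fit. One last seen at Month 18 adds almost nothing to that slope. Growth before the interval plays no part, so if faster growers leave, the fit describes the slower growers who stayed.

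This analysis has real work to do. The 4.2.1.2 slope averages over 24 months, including a first year in which the EM and EOM patients were on the same regimen. The piece-wise analysis is the place where the plan sets out growth rates by interval, including the two intervals after re-randomisation. It is also the listed look at linearity on the raw-area scale, whereas the Year 1 SAP's linearity evidence concerns square-root area. A spurious late slowing would mislead on both.

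**Working it through.** The plan states no figure for this analysis, so there is none to reproduce. The inputs to steps 2, 3 and 4 are assumptions, not figures from the documents.

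**1. Complete data.** A linear spline with knots at Months 6, 12 and 18 has an intercept and four segment slopes, so five parameters per arm. At nominal visit times these are equivalent to five visit means. In a complete test data set the Month 18-24 slope was 2.3049 mm²/year both from the two-visit fit and from the five visit means. Leaving out earlier visits costs nothing in the point estimate until data are missing or visit days vary.

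**2. Dropout that depends on observed growth, one arm.** Assumed inputs:

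- straight-line growth with true mean 2.20 mm²/year
- baseline SD 4 mm², slope SD 0.8 or 1.2, residual SD 0.3 or 0.6
- 5% or 10% dropout at each of Months 18 and 24 (9-19% missing by Month 24)
- dropout log-odds of 0, 0.5 or 1.0 per SD of growth already observed
- 400,000 simulated patients per scenario

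Estimated Month 18-24 slope, as the range over the eight settings in each row:

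| Log-odds per SD | Separate two-visit fit | Joint, unstructured | Joint, random intercept |
|---|---|---|---|
| 0 | 2.200-2.204 | 2.199-2.204 | 2.200-2.205 |
| 0.5 | 2.102-2.187 | 2.198-2.205 | 2.007-2.150 |
| 1.0 | 2.032-2.168 | 2.197-2.202 | 1.873-2.101 |

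Smallest bias of the separate fit: (2.20 - 2.187)/2.20 = 0.6%. Largest: (2.20 - 2.032)/2.20 = 7.6%. For the joint random-intercept model the range is (2.20 - 2.150)/2.20 = 2.3% to (2.20 - 1.873)/2.20 = 14.9%, and it was worse than the separate fit in every scenario with growth-dependent dropout. A random intercept carries each leaver forward at the average of past deviations from the mean, below the level a fast grower had reached.

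A further simulation with 14-17% growth-dependent Year 2 dropout gave Month 12-18 and Month 18-24 slopes of 2.16 and 2.13 under weaker dependence, and 2.12 and 2.04 under stronger dependence, against a true 2.20. The joint unstructured model gave 2.20.

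**3. Treatment difference.** Assumed: 170 Sham and 85 EM patients, true slopes 2.2 and 1.9 (difference -0.30 in every interval), Year 2 dropout 12-16%, 3,000 trials per scenario.

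| Dropout rule | Separate, Month 12-18 | Separate, Month 18-24 |
|---|---|---|
| Depends on growth in Sham only | -0.23 | -0.15 |
| Weaker dependence | -0.27 | -0.23 |
| Same rule in both arms | about right | about right |

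One five-visit unstructured model gave -0.30 in both intervals, and a five-visit model with only a random intercept gave -0.11 and -0.03. Under the same rule in both arms, the separate fits put the Sham slope at 2.12 and then 2.05: (2.20 - 2.12)/2.20 = 3.6% and (2.20 - 2.05)/2.20 = 6.8% too low.

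**4. Covariance between adjacent slopes.** With slope SD s, residual SD e and interval h = 0.5 year, each interval slope has variance s² + 2e²/h² and adjacent slopes have covariance s² - e²/h². For s = 1.2, e = 0.3 the variance is 1.44 + 0.72 = 2.16, the covariance 1.44 - 0.36 = 1.08 and the correlation 0.50. The SE of the change is then √(1 - 0.50) = 0.71 times the value under independence. For s = 0.8, e = 0.6 the correlation is (0.64 - 1.44)/3.52 = -0.23 and the factor is 1.11. Separate fits do not supply this covariance, and assuming independence can err either way.

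**5. A yardstick from the documents.** Protocol 11.3 (0.11 mm) and 4.3.4 (27.38%) imply Sham growth in OPH2003 of 0.11/0.2738 = 0.40 mm/year in square-root area. If that growth is linear at rate b, the raw-area slope rises between consecutive 6-month intervals by 2b² × 0.5 = b² = 0.16 mm²/year. The largest bias in step 2, 2.20 - 2.032 = 0.17, is about one such step in the opposite direction.

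**The case against.** The strongest case against has five parts.

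- *The text does not say separate.* True. The same section says spline, so what the words prove is ambiguity. A reader might infer that separate fits are firmly specified. They are the literal reading of the method sentence, not an explicit instruction.
- *Change of effect can be tested elsewhere.* This stands. A reader might infer that the plan cannot test whether the effect grows or wanes. The model in 4.2.1.3.3 uses all five visits, and its treatment-by-visit contrasts could do so. The plan names no such contrast, and 4.2.1.3.4 promises none.
- *The late treatment difference need not be wrong.* This stands. A reader might infer that the late difference will be distorted. That needs growth-dependent dropout that differs by arm, and nothing in the documents indicates it.
- *Joining the pieces is not what removes the bias.* Largely right. The covariance matters as much: with only a random intercept, a joint model does worse. Section 5.2 refers to a model similar to that of the Year 1 SAP, which is unstructured, but the revised model in 4.2.1.2 names only a subject effect.
- *Section 4.1.2 does not promise validity under missing at random for every supportive analysis.* Fair. It names the mean-growth model and treats sensitivity analyses separately. The piece-wise fits fall short of the general aim stated there, without breaking an explicit commitment.

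What remains is a method sentence that, taken at its word, is less robust than an equally simple alternative.

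**Conclusion.** The point holds in limited form. Read literally, 4.2.1.3.4 gives four two-visit fits that do not condition on earlier growth. If Year 2 dropout depends on that growth, the Month 12-18 and 18-24 slopes within an arm are biased. The Month 18-24 bias is illustratively about 1-8% downward when faster growers leave, and the direction reverses if slower growers leave. This size rests on assumed dropout rates, dependence and variances. There is no bias from this source when dropout is unrelated to earlier growth, and none in complete data at regular visits. Selection in Year 1 belongs to the population definition, not to this analysis. Change of effect over time cannot be tested within the separate fits, but it can within the plan. Severity is low, since no ranked hypothesis visible in the plan depends on this analysis.

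**What to change.** Replace the last sentence of 4.2.1.3.4 with one model on all five visits: a linear spline in days, knots at Months 6, 12 and 18, and arm-specific segment slopes. Adjacent-visit contrasts from the 4.2.1.3.3 model would serve equally.

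State the covariance explicitly: unstructured by visit, as in the Year 1 SAP, which means 5 × 6/2 = 15 parameters. If it fails to converge, fall back on a random intercept and slope. The Year 1 fallback list ends in compound symmetry, which here brings back the random-intercept problem.

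Report the EM-Sham and EOM-Sham difference for each segment with its confidence interval. Add, for each comparison, a joint test (3 degrees of freedom) that the difference is equal across the four segments. Label all of this supportive.

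The cost is a few lines of SAP wording and one model in place of four fits. It needs no new data, and the point estimates do not change when data are complete and visits regular.
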